										vital signs. In the event BMS-986226 administration is delayed, nivolumab or ipilimumab vital signs will be obtained until 60 minutes after completion of the infusion. If any vital sign is abnormal (based on clinician assessment) at the final check, the participant must be observed further for a period of time, as clinically indicated.
	I			I		I		I		

Procedures for Safety Cohort, and Parts A, B, C, D and E ^{a,b}			C1			C2 to beyond	C2 Only	C2 Only		Notes
Procedure	D1	D2	D8 ± 1 days	D15 ±1 days	D22 ± 1 days	D1	D2	D8 ±1 days	EOT c,d,e	
Laboratory Tests										See Section 9.4.4. On-study laboratory tests (including pregnancy testing) to be done on site/local within 72 hours prior to dosing on Day 1 of each cycle.
Chemistry	Х	Х	Х	Х	Х	Х	Х	Х	Х	See note in Table 2-1. On-treatment Glucose is not required to be fasting. Every cycle on Day 1. For parts B1 and C1, Cycle 2 Day 2 only and Cycle 2 Day 8 only, assessments should take place on Cycle 4 Day 2 and Cycle 4 Day 8.
CBC with Differential and Platelets	Х	Х	Х	Х	Х	Х	Х	Х	Х	Should also be collected at each time point where samples are collected For parts B1 and C1, Cycle 2 Day 2 only and Cycle 2 Day 8 only assessments should take place on Cycle 4 Day 2 and Cycle 4 Day 8.
Thyroid Function Tests	Х					X (see notes)				To include TSH with reflex testing (free T3 and free T4), if applicable. Results should be examined by the investigator or appropriate designee within 48 hours of dose administration. To be performed during odd cycles (eg, Cycles 1, 3, and 5) only.

Procedures for Safety Cohort, and Parts A, B, C, D and E ^{a,b}			C2 to beyond	C2 Only	C2 Only		Notes			
Procedure	D1	D2	D8 ± 1 days	D15 ± 1 days	D22 ± 1 days	D1	D2	D8 ±1 days	EOT c,d,e	
Urinalysis					As clinic	cally indica	See note in Table 2-1. See Section 9.4.4.			
Pregnancy Test (WOCBP)	Х					Х			X	Serum/urine pregnancy test must be performed (urine pregnancy test: minimum sensitivity 25 IU/L or equivalent units of hCG) within 24 hours prior to administration of study treatment. If the pregnancy test result is positive, hold all study treatments and perform confirmatory testing. If pregnancy is confirmed, permanently discontinue all study treatment and immediately notify BMS Medical Monitor/Study Director or designee (see Section 9.2.5).
AE Reporting and Conco	mitant M	ledicatio	n Assessm	ents						
Concomitant Medication Assessments		Х								Review prior to dosing.

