5.1.2 Treatment Phase

The treatment phase in the Preliminary Safety Cohort and Part A consists of up to six 4-week treatment cycles (1 cycle = 28 days). In the Preliminary Safety Cohort and Part A, each treatment cycle will consist of BMS-986226 monotherapy for a total of 24 weeks.

Dose levels for Parts B and C will be determined based on all available safety (clinical and laboratory) and PK data, as well as changes in peripheral target engagement markers (eg, ICOS

downregulation on T cells and ICOS + B cells) from previous and completed portion of current cohorts, and will be guided by the BLRM/BLRM-Copula model whenever applicable.

In Parts B1 and C1, 4 week cycles will be used, such that BMS986226 + nivolumab or ipilimumab will be administered starting on Cycle 1 Day 1. Nivolumab and ipilimumab will be administered on Day 1 of each cycle. BMS-986226 will be administered Q12W, or on Day 1 of every third cycle (Cycle 1 Day1, Cycle 4, Day1, Cycle 7 Day1, etc.). Participants on Parts B1 and C1 may continue treatment for up to a total of 2 years.

The treatment phase in Parts B2 and C2 will consist of BMS-986226 + nivolumab or ipilimumab administered on Day 1 of each cycle and will be enrolled if additional safety, PK, or PD data is required to optimize dose and/or schedule selection. In parts B2 and C2 BMS-986226 will be administered Q4W and participants may continue treatment for a total of 2 years.

Following each treatment cycle, the decision to treat a participant with additional cycles of study treatment will be based on tumor assessment evaluations performed every 8 weeks $(Q8W \pm 1 \text{ week})$ and completed before the first dose in the next cycle. Tumor progression or response endpoints will be assessed using Response Evaluation Criteria In Solid Tumors (RECIST) v1.1 (Appendix 5) or PCWG3, for prostate only (Appendix 11).

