Dose-limiting Toxicities in Combination Cohorts (Parts B and C)

For the purpose of ensuring safety, DLTs will be defined based on the incidence, intensity, and duration of AEs for which no clear alternative cause is identified. The DLT period will be 35 days (5 weeks) in Parts B and C.

For the purpose of participant management, any AE that meets DLT criteria (Section 7.3.2), regardless of the cycle in which it occurs, will lead to temporary hold of study treatment.

Participants who withdraw from the study during the DLT evaluation period for reasons other than a DLT may be replaced with a new participant at the same dose level.

Re-challenge of participants experiencing a DLT will be evaluated on a case-by-case basis, once the AE returns to baseline or Grade 1, after specific consultation and agreement between the investigator and BMS Medical Monitor/Study Director (or designee) in settings where benefit/risk justify re-administration of study treatment (see Section 7.3.5).

AEs will be graded according to the NCI CTCAE v4.03.²⁷

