Participants experiencing a DLT will enter the safety follow-up period of the study. DLTs occurring after the 4-week DLT observation period for the Preliminary Safety Cohorts or 5-week DLT observation period for Parts A, B and C will be accounted for in determining the MAD for the combination part.

AEs will be graded according to the NCI CTCAE v4.03²⁷, as listed below:

A. Hepatic Non-hematological DLT

Any one of the following study treatment-related events will be considered a hepatic DLT:

- Any Grade \geq 3 elevation of AST, ALT, or total bilirubin.
- Grade 2 AST or ALT with symptomatic liver inflammation (eg, right upper quadrant tenderness, jaundice, pruritus).
- AST or ALT > 3× ULN and concurrent total bilirubin > 2× ULN without initial findings of cholestasis (elevated serum alkaline phosphatase [ALP] [eg, findings consistent with Hy's law or FDA definition of potential drug-induced liver injury or potential drug-induced liver injury [p-DILI]). Note that this special category of DLT uses ULN rather than Common Toxicity Criteria (CTC) grade for definition.

B. Non-hepatic Non-hematological DLT

Any of the following events will be considered a non-hepatic non-hematological DLT:

- Any Grade 2 drug-related uveitis or eye pain or blurred vision that does not respond to topical therapy and does not improve to Grade 1 severity ≤ 2 weeks *or* requires systemic treatment.
- Grade 3 drug-related uveitis, pneumonitis, bronchospasm, myocarditis, neurologic toxicity, hypersensitivity reaction, or infusion reaction of any duration will require discontinuation.
- Any Grade 3 or greater nondermatologic, nonhepatic nonhematological study treatment-related toxicity will be considered a DLT, with the following specific exceptions:
 - Grade 3 or Grade 4 electrolyte abnormalities that are not complicated by associated clinical adverse experiences, last \leq 72 hours, and either resolve spontaneously or respond to conventional medical intervention
 - Grade 3 nausea, vomiting, or diarrhea that lasts less than 72 hours (without steroid therapy) and either resolves spontaneously or responds to conventional medical intervention
 - Isolated Grade 3 elevation of amylase or lipase not associated with clinical or radiographic evidence of pancreatitis

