10 STATISTICAL CONSIDERATIONS

10.1 Sample Size Determination

10.1.1 Preliminary Safety Cohorts and Dose Escalation (Part A)

Two single participants will be treated at BMS-986226 2 mg and 8 mg, respectively, in the Preliminary Safety Cohorts. Additional participants may be enrolled in the Preliminary Safety Cohorts at each dose level to gather additional information on the safety, PK, and PD profile. Approximately 3 participants will be treated at the starting dose levels of BMS-986226 in Part A. During the dose-escalation phase, an adaptive dose-escalation scheme (BLRM for monotherapy and BLRM-Copula for combination therapy) employing the escalation with overdose control (EWOC) principle will be used. The method is fully adaptive, makes use of all the information available at the time of each dose assignment, not just data from the current dose level, and directly addresses the ethical need to control the probability of overdosing. The targeted toxicity rate in this study is in the range of 16% to 33%. The boundary is similar to the toxicity boundary used by a rule-based design (ie, 3 + 3 design) in that a minimum is set at 16% (approximately 1 in 6) DLT rate and at a maximum at 33% (approximately 2 in 6) DLT rate. The use of the EWOC principle limits the risk of exposing participants in the next cohort to an unsafe dose by ensuring the posterior probability of the DLT rate exceeding 33% at any dose is capped at 30%.

Due to the nature of the dose escalation process, the exact number of participants to be treated at each dose level cannot be precisely determined. The maximum number of participants to be treated in Part A will be approximately 30 for dose escalation. However, simulation studies with various scenarios show that the expected number of DLT-evaluable participants is approximately 20 participants or less (Appendix 10).

While the BLRM/BLRM-Copula will use DLT information from the DLT period only, clinical assessment will take into consideration the totality of available data, including PK/PD from all treated participants encompassing monotherapy and combination therapy, in assigning a dose level for the next cohort of 3 participants. At most, 12 DLT-evaluable participants will be treated at each dose level. Additional participants (up to a total of 12) may be treated at or any dose level below the estimated MTD for further evaluation of safety, PK, or PD parameters as required.

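### In Parts B1 and C1 no chemistry is scheduled between the second nivolumab or ipilimumab dose (Day 29) and the close of the 35-day DLT window

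*Combined protocol and SAP*

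**What the plan says.** Table 2-2 (On-treatment Procedural Outline) marks chemistry on Cycle 1 Days 1, 2, 8, 15 and 22, on Day 1 of each later cycle, and on Cycle 2 Days 2 and 8. Its note moves the last two for Parts B1 and C1: "For parts B1 and C1, Cycle 2 Day 2 only and Cycle 2 Day 8 only, assessments should take place on Cycle 4 Day 2", with the Day 8 draw going to Cycle 4 Day 8. Day 1 laboratory work is "to be done on site/local within 72 hours prior to dosing on Day 1 of each cycle", so it precedes the dose.

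Section 5.1.2 sets the dosing for B1 and C1. For the partner drugs: "Nivolumab and ipilimumab will be administered on Day 1 of each cycle". For the study drug: "BMS-986226 will be administered Q12W, or on Day 1 of every third cycle". The paragraph on DLTs in the combination cohorts, at the end of Section 5.1.2.3, states: "The DLT period will be 35 days (5 weeks) in Parts B and C". In Section 7.3.2 the hepatic DLTs include any Grade 3 or higher "elevation of AST, ALT, or total bilirubin", together with a category defined by multiples of the upper limit of normal.

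On what the dose model uses, Section 10.1.1 says: "While the BLRM/BLRM-Copula will use DLT information from the DLT period only". Appendix 10, Section 5, says the same for the combination cohorts.

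**The concern.** The relocated draws follow the second BMS-986226 dose, which in B1/C1 falls on Cycle 4 Day 1. The partner drug stays on a 4-week schedule and the DLT window did not move. The second partner dose is thus inside the window with no scheduled laboratory check after it. Covering that dose appears to be part of the window's purpose: Section 7.3.2 accepts two partner doses as one route to DLT evaluability, and the Revised Protocol 02 rationale in Appendix 12 describes the 5-week period as spanning two partner doses.

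BMS-986226 would still be present at that time. With the 25-day half-life predicted in Section 3.2.2.5, simple exponential decay leaves 0.5^(28/25) = 46% after 28 days, so the last week of the window is combination exposure.

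DLT incidence is a component of the primary endpoint and drives the BLRM-Copula. B1 and C1 are the lead combination cohorts, since B2 and C2 open only at dose levels already tested there. Each B1/C1 dose level has about 6 evaluable participants, so incomplete ascertainment matters. Purely laboratory events without symptoms are the ones at risk, because only a blood draw reveals them.

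**Working it through.** **Inputs.** 28-day cycles, with the first dose on Day 1 and doses on nominal days; DLT window read as Days 1 to 35 (Section 5.1.2.3); Day 1 labs up to 72 hours before dosing and Day 8 visits within 1 day (Table 2-2); about 6 evaluable participants per B1/C1 dose level (Section 10.1.2).

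**1. The plan's own figure.** Section 10.1.2 gives about 80% probability of seeing an AE with a true rate of 24% among 6 participants. 1 − (1 − 0.24)^6 = 0.807, so the figure reproduces and is not in dispute.

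**2. Visit days.** Study day = (cycle − 1) × 28 + cycle day.

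| Visit | Study day | In the 35-day window? |
|---|---|---|
| C2D1 (second partner dose) | 29 (labs Days 26–29, pre-dose) | yes |
| C2D2 | 30 | yes |
| C2D8 | 36 (35–37) | at the edge |
| C3D1 | 57 (labs Days 54–57, pre-dose) | no |
| C4D1 (second BMS-986226 dose, B1/C1) | 85 | no |
| C4D2 | 86 | no |
| C4D8 | 92 | no |

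**3. Scheduled chemistry after the Day 29 dose and before C3D1.** In B2/C2 there are two draws, one clearly in the window (Day 30) and one at its edge (Day 36, or Day 35 if drawn a day early). In B1/C1 there are none. The moved draws fall 86 − 35 = 51 and 92 − 35 = 57 days after the window closes. From the second partner dose to the next scheduled panel is 54 − 29 = 25 to 57 − 29 = 28 days.

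**4. Share of the window affected.** Days 30–35 are 6/35 = 17% of the window; counting Day 29 as well, 7/35 = 20%. This is a share of days, not of events.

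**5. What happens to an event first seen at C3D1.** It would be dated after the window. Section 10.1.1 and Appendix 10, Section 5, restrict the model to DLT-period data. Section 7.3.2 lets later AEs inform the model if the sponsor, medical monitor and investigators agree. The same section counts later DLTs toward the combination MAD. The event is therefore not lost to the trial, but its entry into the model is discretionary.

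**6. Sensitivity, by assumption.** The documents give neither the share of DLTs that are laboratory-only and silent nor their onset times. Suppose a fraction f of all events were missed. The detection probability at n = 6 becomes 1 − (1 − 0.24(1 − f))^6:

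| f | Probability of seeing at least one |
|---|---|
| 0 | 80.7% |
| 5% | 78.8% |
| 10% | 76.8% |
| 20% | 72.2% |
| 30% | 66.8% |

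Under uniform onset over the window, f could not exceed 7/35 = 20% even if every event were laboratory-only and none were caught otherwise. A larger f needs onset to cluster after the second dose. The table shows how the quantity scales and is not an estimate of the bias.

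**The case against.** The Cycle 2 Day 2 and Day 8 panels were added in Revised Protocol 03 to monitor effects of BMS-986226 (Appendix 12), and for a 12-weekly drug Cycle 4 serves that aim. Section 3.3 commits to weekly chemistry for 4 weeks only, and B1/C1 meet it. An interval of about 4 weeks between panels is also ordinary later on: the other parts have Day 1 chemistry only from Cycle 3. All of this is correct and explains the note. It does not explain why a 5-week window containing a second partner dose has no laboratory check after that dose.

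A reader might infer that laboratory-defined DLTs in this period go uncounted. The documents do not support that. Section 9 provides for tests as clinically indicated, and an in-window result would count. Persistent elevations remain visible at C3D1. Later DLTs count toward the MAD, and later AEs may enter the model. The primary endpoint in Table 4-1 states no window.

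A reader might also infer that 20% of such DLTs are lost, or that the comparison of 12-weekly with 4-weekly dosing is biased toward the former. The 20% holds only under uniform onset and no other detection. On the comparison, follow-up is unequal, but no formal test is planned, schedule selection for Parts D and E uses all available data (Section 5.1.2.4), and B2/C2 receive a second BMS-986226 dose inside their own window. B2/C2 also have only one clearly in-window post-dose panel, one day after dosing.

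The CBC row carries the same relocation, but it also asks for collection alongside other samples whose type is missing from this copy. Whether CBC is covered at Cycle 2 Day 8 cannot be judged.

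**Conclusion.** The scheduling gap stands. It follows from Table 2-2, the dosing schedule and the length of the window by day arithmetic alone, assuming doses on nominal days. A silent laboratory-defined DLT arising after the second partner dose may go undetected, or be dated after the window. This can only push the observed in-window DLT rate in B1/C1 downward. The size of that bias cannot be derived from the documents, and it depends on asymptomatic events that are transient or found late.

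The in-window loss relative to B2/C2 is one draw on Day 30, plus an edge draw on Day 36 (35–37). If the window were counted as 35 elapsed days after the first dose, nominal Cycle 2 Day 8 would fall on its last day; the text does not settle this.

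That one missed event moves a cohort of 6 from 2/6 to 1/6, roughly the 33% and 16% limits, is true arithmetic, but it presumes that such an event occurs and is missed. The point therefore supports a cheap improvement to a primary-endpoint component. It does not show that dose decisions in B1/C1 would be wrong.

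**What to change.** In the Table 2-2 chemistry note, make the Cycle 4 Day 2 and Day 8 draws for B1/C1 additional to a Cycle 2 post-dose panel instead of a replacement for it. Table 9.5-2 already has a PK blood draw at Cycle 2 Day 8 in these parts, so no new visit is needed. Because that visit is nominally Day 36, do one of the following:

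- time it to Day 35 within the existing 1-day allowance;
- state that its result counts in the DLT assessment;
- retain Cycle 2 Day 2 (Day 30), which is clearly inside the window.

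Reconcile three places: Table 2-2, the 5-week DLT window, and Section 3.3. Section 3.3 promises weekly labs for 4 weeks and weekly symptom-directed examinations for 5 to 6 weeks, yet Table 2-2 marks no such examination on Cycle 2 Day 2 or Day 8. Say in the CBC row whether Cycle 2 Day 8 is already covered for B1/C1.

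Cost: one edited note and one additional routine chemistry panel per B1/C1 participant.

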3 INTRODUCTION

CA021002 is a Phase 1/2, first-in-human (FIH), ascending, multiple-dose study of BMS-986226, an Inducible T-cell - COStimulator (ICOS; cluster of differentiation [CD]278) agonist monoclonal antibody (mAb), in humans with advanced/metastatic solid tumors as monotherapy or in combination with either nivolumab (programmed death 1 [PD-1] receptor blocking mAb) or ipilimumab (cytotoxic T lymphocyte-associated antigen-4 [CTLA-4], an activation-induced T-cell surface molecule that binds CD80 and CD86).

This study will evaluate the safety profile, tolerability, pharmacokinetics (PK), and pharmacodynamics (PD) of intravenous (IV) doses of BMS-986226 administered as monotherapy or in combination with either nivolumab or ipilimumab in participants with advanced solid tumors, including but not limited to, cervical cancer (CC), colorectal cancer (CRC), head and neck squamous cell carcinoma (HNSCC), melanoma (MEL), non-small cell lung cancer (NSCLC), adenocarcinoma of the prostate (PRC), renal cell carcinoma (RCC), triple negative breast cancer (TNBC) and urothelial carcinoma (UCC).

3.1 Study Rationale

Antibody-based therapy for cancer has become established in recent years and is now one of the most successful and important strategies for treating patients with hematological malignancies and advanced solid tumors.¹ Aside from targeting antigens that are involved in cancer cell proliferation and survival, antibodies can also function to either activate or inactivate immunological pathways that are important in cancer immune surveillance.² It is now clear that an antigen-specific anti-cancer immune response is the result of a complex dynamic interplay between antigen presenting cells (APCs), T lymphocyte cells (T cells), and the target cancer cells. The critical balance of T-cell activity that dictates whether endogenous anti-tumor immune responses will be effective are largely understood to be controlled by antigen-specific stimuli sensed by the T-cell receptor and by the combined activity of both positive (co-stimulatory) and negative (co-inhibitory) T-cell surface molecules.³ Within the past decade, antibodies against these key receptors have been designed and evaluated in the clinic with impressive results, heralding the onset of immunotherapy as a key pillar of anti-cancer therapy.⁴

The most extensively studied immunotherapies in cancer target the negative regulatory receptors CTLA-4 or PD-1.⁵ Inhibition of these negative regulatory receptors, referred to as immune checkpoint blockade, results in the enhanced activation of T-cell responses and potent anti-tumor activity in nonclinical models. Studies with CTLA-4 blockade provided the first clinical evidence of improvement in overall survival (OS) with immune modulatory anti-cancer therapy in patients with metastatic melanoma.^{6,7} Following that, Topalian et al showed that anti-PD-1 antibody

therapy resulted in objective responses in patients with melanoma, NSCLC, and renal cell carcinoma (RCC).⁸

Subsequent to the success of anti-tumor treatment with CTLA-4 and PD-1 pathway-blocking agents, the field of tumor immunotherapy is expanding rapidly. In addition to blocking co-inhibitory pathways, activating co-stimulatory pathways to potentiate anti-tumor immune responses is being considered as a promising approach.⁹ With recent emerging clinical evidences of significant anti-tumor activity of single-agent immunotherapies, combination therapies are now explored because they could lead to greater depth of response and OS. This has been observed with the combination therapy of anti-PD-1 and anti-CTLA-4 antibodies in patients with advanced melanoma. It also raises the possibility that combining checkpoint blocking antibodies with agonistic antibodies targeting T-cell co-stimulatory molecules could be beneficial. Nonclinical data evaluating this type of treatment combination in mouse tumor models indicate that combination treatment indeed leads to enhanced anti-tumor activity compared with single-agent-treatment.

Administration of ipilimumab has been shown to up-regulate ICOS expression on the surface of CD4 and CD8 effector T cells in patients with superficial bladder cancer and advanced melanoma.¹⁰ Patients with \geq 2-fold increase in percentage of circulating CD4⁺ICOS^{hi} expression that was sustained at Week 12 showed clinical benefit, while patients with < 2-fold increase did not, thus suggesting a role for ICOS+ T cells in supporting anti-tumor activity after administration of ipilimumab (n = 14).

Nivolumab treatment results in increased ICOS gene expression in tumor biopsies in patients with both RCC and melanoma.^{11,12} The increase in ICOS expression after both ipilimumab and nivolumab treatment suggests that the ICOS pathway is an appealing target for an agonist antibody in combination with either nivolumab or ipilimumab, alone or as a combination.

ICOS costimulation potently induces T-cell activation and cytokine production, and agonism of ICOS on T-effector cells (Teffs) should further enhance antitumor activity. The activity of an ICOS agonist may provide the most benefit in combination with checkpoint inhibitors that induce ICOS expression (eg, ipilimumab or nivolumab) and in patients whose T cells are not receiving an optimal costimulatory signal through ICOS due to low expression of Inducible T-cell COStimulator ligand (ICOS-L) at the tumor site.

In this study, participants with advanced tumors will be treated with BMS-986226 (an agonistic antibody targeting ICOS) monotherapy or BMS-986226 in combination with nivolumab (a checkpoint blocking antibody [anti-PD-1 antibody]) or ipilimumab (a checkpoint blocking antibody [anti-CTLA-4 antibody]) to take advantage of this enhanced anti-tumor effect.

